## **Appendix 2. Kellgren-Lawrence Grading Scale**

### **Kellgren-Lawrence Grading Scale**

The Kellgren-Lawrence grading system is radiological classification of knee osteoarthritis. It is based on x-rays and consists of normal, Grade 1, Grade 2, Grade 3, and Grade 4.

- Grade 1: Unlikely narrowing of the joint space, possible osteophytes
- Grade 2: Small osteophytes, possible narrowing of the joint
- Grade 3: Multiple, moderately sized osteophytes, definite joint space narrowing, some sclerotic areas, possible deformation of bone ends
- Grade 4: Multiple large osteophytes, severe joint space narrowing, marked sclerosis and definite bony end deformity.

### Appendix 3. WOMAC (Western Ontario and McMaster Universities Arthritis Index)

#### Section A

## PAIN

Think about the pain you felt in your \_\_\_\_\_ (study joint) caused by your arthritis during the last 48 hours.

(Please mark your answers with an “x”.)

QUESTION: How much pain have you had ...					Study Coordinator Use Only
1. when walking on a flat surface?					PAIN1 _____
none	mild	moderate	severe	extreme	
					
2. when going up or down stairs?					PAIN2 _____
none	mild	moderate	severe	extreme	
					
3. at night while in bed? (that is – pain that disturbs your sleep)					PAIN3 _____
none	mild	moderate	severe	extreme	
					
4. while sitting or lying down?					PAIN4 _____
none	mild	moderate	severe	extreme	
					
5. while standing?					PAIN5 _____
none	mild	moderate	severe	extreme	
					

## Section B

### STIFFNESS

Think about the stiffness (not pain) you felt in your \_\_\_\_\_ (study joint) caused by your arthritis during the last 48 hours.

Stiffness is a sensation of **decreased** ease in moving your joint.

(Please mark your answers with an “x”.)

6. How **severe** has your stiffness been **after you first woke up** in the morning?

none      mild      moderate      severe      extreme  
                       

7. How **severe** has your stiffness been after sitting or lying down or while resting **later in the day**?

none      mild      moderate      severe      extreme  
                       

Study Coordinator  
Use Only

STIFF6 \_\_\_\_\_

STIFF7 \_\_\_\_\_

## Section C

### DIFFICULTY PERFORMING DAILY ACTIVITIES

Think about the difficulty you had in doing the following daily physical activities caused by the arthritis in your \_\_\_\_\_ (study joint) during the last 48 hours. By this we mean **your ability to move around and take care of yourself.**

(Please mark your answers with an “x”.)

#### QUESTION: How much difficulty have you had ...

8. when going down the stairs?

none	mild	moderate	severe	extreme
				

9. when going up the stairs?

none	mild	moderate	severe	extreme
				

10. when getting up from a sitting position?

none	mild	moderate	severe	extreme
				

11. while standing?

none	mild	moderate	severe	extreme
				

12. when bending to the floor?

none	mild	moderate	severe	extreme
				

13. when walking on a flat surface?

none	mild	moderate	severe	extreme
				

Study Coordinator  
Use Only

PFTN8 \_\_\_\_\_

PFTN9 \_\_\_\_\_

PFTN10 \_\_\_\_\_

PFTN11 \_\_\_\_\_

PFTN12 \_\_\_\_\_

PFTN13 \_\_\_\_\_

## DIFFICULTY PERFORMING DAILY ACTIVITIES

Think about the difficulty you had in doing the following daily physical activities caused by the arthritis in your \_\_\_\_\_ (study joint) during the last 48 hours. By this we mean **your ability to move around and take care of yourself**.

(Please mark your answers with an “x”.)

### QUESTION: How much difficulty have you had ...

14. getting in or out of a car, or getting on or off a bus?

none	mild	moderate	severe	extreme
				

15. while going shopping?

none	mild	moderate	severe	extreme
				

16. when putting on your socks or panty hose or stockings?

none	mild	moderate	severe	extreme
				

17. when getting out of bed?

none	mild	moderate	severe	extreme
				

18. when taking off your socks or panty hose or stockings?

none	mild	moderate	severe	extreme
				

19. while lying in bed?

none	mild	moderate	severe	extreme
				

Study Coordinator  
Use Only

PFTN14 \_\_\_\_\_

PFTN15 \_\_\_\_\_

PFTN16 \_\_\_\_\_

PFTN17 \_\_\_\_\_

PFTN18 \_\_\_\_\_

PFTN19 \_\_\_\_\_

## DIFFICULTY PERFORMING DAILY ACTIVITIES

Think about the difficulty you had in doing the following daily physical activities caused by the arthritis in your \_\_\_\_\_ (study joint) during the last 48 hours. By this we mean **your ability to move around and take care of yourself**.

(Please mark your answers with an “x”.)

### QUESTION: How much difficulty have you had ...

20. when getting in or out of the bathtub?

none	mild	moderate	severe	extreme
				

21. while sitting?

none	mild	moderate	severe	extreme
				

22. when getting on or off the toilet?

none	mild	moderate	severe	extreme
				

23. while doing heavy household chores?

none	mild	moderate	severe	extreme
				

24. while doing light household chores?

none	mild	moderate	severe	extreme
				

Study Coordinator  
Use Only

PFTN20 \_\_\_\_\_

PFTN21 \_\_\_\_\_

PFTN22 \_\_\_\_\_

PFTN23 \_\_\_\_\_

PFTN24 \_\_\_\_\_

Study Coordinator:

Signature: \_\_\_\_\_ Date: \_\_\_\_\_

#### Appendix 4. VAS (Visual Analogue Scale) for Pain

Site No: \_\_

Subject No: \_\_ \_\_

[figure not shown]
Subject Initials: \_\_ \_\_ \_\_

Visit (circle one): Baseline M1 M3 M6 M9 M12 ET ( / / ) Final FU ( / / )

Pain 100mm Visual Analogue Scale

Please mark on the scale below how you feel your pain rates today as the following example:

*Example:*

Marked Length (mm) \_\_\_\_\_

Study Coordinator:

Signature: \_\_\_\_\_ Date: \_\_\_\_\_

## Appendix 5. Lysholm Knee Scale

Site No: \_\_

Subject No: \_\_ \_\_

Subject Initials: \_\_ \_\_ \_\_

Visit (circle one): Baseline M1 M3 M6 M9 M12 ET ( / / ) Final FU ( / / )

This questionnaire has been designed to give your Physical Therapist information as to how your knee pain has affected your ability to manage everyday life. Below are common complaints that people frequently have with their knee problems. Please answer every section and mark only **ONE** box which best describes your condition at this moment.

### I. LIMP:

- I have no limp when I walk. (5)
- I have a slight or periodical limp when I walk. (3)
- I have a severe and constant limp when I walk. (0)

### II. USING CANE OR CRUTCHES:

- I do not use a cane or crutches. (5)
- I use a cane or crutches with some weight-bearing. (2)
- Putting weight on my hurt leg is impossible. (0)

### III. LOCKING SENSATION IN THE KNEE:

- I have no locking and no catching sensations in my knee. (15)
- I have catching sensations but no locking sensations in my knee. (10)
- My knee locks occasionally. (6)
- My knee locks frequently. (2)
- My knee feels locked at this moment. (0)

### IV. GIVING WAY SENSATION FROM THE KNEE:

- My knee never gives way. (25)
- My knee rarely gives way only during athletics or other vigorous activities. (20)
- My knee frequently gives way during athletics or other vigorous activities and in turn, I am unable to participate in these activities. (15)
- My knee often gives way during daily activities. (5)
- My knee gives way every step I take. (0)

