### V. PAIN:

- I have no pain in my knee. (25)
- I have intermittent or slight pain in my knee during vigorous activities. (20)
- I have marked pain in my knee during vigorous activities. (15)
- I have marked pain in my knee during or after walking more than 1 mile. (10)
- I have marked pain in my knee during or after walking less than 1 mile. (5)
- I constant pain in my knee. (0)

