6.2.4 Lysholm Knee Scoring Scale

Lysholm knee scoring scale will be collected at Visits 3, 4, 5, 6, 7 and 8 (Baseline, M1, M3, M6, M9 and M12) or Early Termination (only if the subject is early terminated after Visit 3) or Final Follow-up Visit. Summary statistics of lysholm knee scoring scale will be presented by visit and treatment group. The change from baseline will also be calculated and represented in summary table.

- ① Change of Lysholm Knee Scoring Scale from baseline at Month 6 (JointStem group vs. positive control group)

This secondary efficacy endpoint will be analyzed with an ANCOVA with factors of treatment and the baseline of Lysholm Knee Scoring Scale as a covariate. Model-based LS Means of the differences between study and control groups, along with 95% CI and p-value will be provided.

- ② Change of Lysholm Knee Scoring Scale from baseline at Months 6, 9 and 12 (JointStem group)

Change of Lysholm Knee Scoring Scale from baseline at Months 6, 9 and 12 will be analyzed using paired t-test. (two-sided test, $\alpha=0.05$) with the null hypothesis equal to zero. The number of patients, mean, standard deviation, minimum (min) and maximum (max) values for the baseline, months 6, months 9, months 12 and change from baseline will be calculated and reported in summary table. The p-value will also be provided. Shapiro-Wilks test will be used to test the normality of change of Lysholm Knee Scoring Scale from baseline at Months 6, 9 and 12. If change of Lysholm Knee Scoring Scale from baseline at Months 6, 9 and 12 doesn’t satisfy normal distribution, Wilcoxon signed rank test will be performed.

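### The printed Lysholm giving-way item has no box for giving way that happens in daily activities but less than often, so such a subject must be scored 15 or 5

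*Protocol*

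**What the plan says.** Protocol Appendix 5, item IV, offers five boxes (the number ending each quote is the printed score):

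- 25 points: no giving way at all.
- 20 points: rare, and confined to sport or similar exertion.
- 15 points, the lowest box tied to sport: "My knee frequently gives way during athletics or other vigorous activities and in turn, I am unable to participate in these activities. (15"
- 5 points, the next box down: "My knee often gives way during daily activities. (5"
- 0 points: giving way with each step.

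The form's instruction contains the words "Please answer every section and mark only"; the subject is to choose a single box, the one that fits the present condition best. Protocol section 3.6.5 has subjects complete the questionnaires alone.

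The only other 25-point item, Pain (item V), has six boxes at 25, 20, 15, 10, 5 and 0. Its 10-point box is "I have marked pain in my knee during or after walking more than 1 mile. (10".

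The Lysholm total is a secondary endpoint. Protocol section 6.1.5 and SAP section 6.2.4 compare the arms at Month 6 by ANCOVA with baseline Lysholm as covariate. For the JointStem arm the SAP adds: "Change of Lysholm Knee Scoring Scale from baseline at Months 6, 9 and 12 will be analyzed using paired t-test". That comparison uses a two-sided level of 0.05, with the Wilcoxon signed rank test as fallback.

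**The concern.** The 20 and 15 boxes are tied to athletics or vigorous activity. The only boxes about daily life or ordinary walking are the two lowest, for giving way that is frequent or happens at every step. A subject whose knee gives way now and then in daily life is worse than the 15 box describes and better than the 5 box describes.

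Two other features of the form suggest that a level may have been dropped. Pain, with the same 25-point range, has a 10-point level where item IV has none. The locking item (III) scores occasional locking (6) separately from frequent locking (2), a distinction that item IV does not make for daily activities.

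At stake is a tested secondary endpoint in which this item carries 25 of 100 points. A subject in the unlisted state is mis-scored at that visit, and the direction depends on which neighbouring box is marked. A real improvement from frequent to occasional giving way in daily life is recorded either as nothing or as a two-box jump.

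**Working it through.** **Inputs.** Box scores from Protocol Appendix 5, items I to VIII. Planned arm sizes of 20 JointStem and 10 control from Protocol section 6.2. The value *m* of the unlisted state is not in the documents, so it is treated as an assumption with a range.

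**1. The form's stated maximum.** Sum of the top boxes: 5 + 5 + 15 + 25 + 25 + 10 + 10 + 5 = 100, which reproduces the printed maximum. An intermediate level in item IV would not alter this sum, so the total cannot reveal whether a level is missing.

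**2. Steps between adjacent boxes.**

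| Item | Boxes | Steps |
|---|---|---|
| I Limp | 5, 3, 0 | 2, 3 |
| II Cane or crutches | 5, 2, 0 | 3, 2 |
| III Locking | 15, 10, 6, 2, 0 | 5, 4, 4, 2 |
| IV Giving way | 25, 20, 15, 5, 0 | 5, 5, **10**, 5 |
| V Pain | 25, 20, 15, 10, 5, 0 | 5, 5, 5, 5, 5 |
| VI Swelling | 10, 6, 2, 0 | 4, 4, 2 |
| VII Stairs | 10, 6, 2, 0 | 4, 4, 2 |
| VIII Squatting | 5, 4, 2, 0 | 1, 2, 2 |

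The 15-to-5 step is the largest on the form.

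**3. Error in the score at one visit.** Marking 15 gives an error of 15 − *m*; marking 5 gives 5 − *m*. Their sizes sum to (15 − *m*) + (*m* − 5) = 10 for any *m* between 5 and 15.

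| Assumed *m* | Marks 15 | Marks 5 |
|---|---|---|
| 7.5 | +7.5 | −2.5 |
| 10 | +5 | −5 |
| 12.5 | +2.5 | −7.5 |

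The central value 10 is the midpoint of 15 and 5, and matches the Pain item's level at that rank.

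**4. Error in the change score.** This is the error at follow-up minus the error at baseline.

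| Situation of one subject | Error in change | Shift in arm mean, n=20 | Shift in arm mean, n=10 |
|---|---|---|---|
| In the unlisted state at both visits, same box | 0 | 0 | 0 |
| In the unlisted state at both visits, different boxes | 10 (any *m*) | 10/20 = 0.5 | 10/10 = 1.0 |
| In the unlisted state at one visit only, *m* = 10 | 5 | 5/20 = 0.25 | 5/10 = 0.5 |

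For the last row, errors of 2.5 to 7.5 points give 2.5/20 = 0.125 to 7.5/20 = 0.375 in the JointStem arm, and 0.25 to 0.75 in the control arm.

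**5. A real change.** Moving from frequent (5) to occasional (10, assumed) giving way in daily life is worth +5. The printed form records 5 − 5 = 0 or 15 − 5 = +10.

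**6. Several subjects.** The documents give no frequency. As an illustration, if 2 to 4 of 20 JointStem subjects each had a 5-point error at one visit only, all in the same direction, the mean change would shift by 2 × 0.25 = 0.5 to 4 × 0.25 = 1.0 points. Errors in opposite directions would partly cancel.

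**The case against.** The case against giving this much weight is substantial, and most of it stands.

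- **A reader might infer that such a subject has no valid answer.** The documents do not support that. The form asks for the best-fitting box, so a nearest box can be marked and no data go missing. The defect is coarse scoring.
- **A reader might infer that every affected subject shifts the mean change.** The same box at both visits cancels. A shift needs the state at one visit only, or different boxes at the two visits.
- **A reader might infer a bias in favour of JointStem.** Nothing shows one. Both arms use the same form, so in the Month 6 ANCOVA the effect would mostly be added noise.
- **A reader might take the Pain item as proof that a 10-point box was dropped.** It is not proof. Unequal steps are common on this form, and other items also leave gaps: Limp goes straight from slight or periodical to severe and constant, and Pain has no box for slight pain in daily activities. The occasional/frequent split in the locking item does point the other way.
- **Giving way is also captured elsewhere.** IKDC item 7 asks for the highest activity level free of significant giving way, and IKDC is a secondary endpoint with the same ANCOVA and paired analyses. This limits the loss of information but does not repair the Lysholm score.
- **Few subjects may be affected.** Exclusion criterion 2 removes unstable knees. It applies at entry only and gives no threshold, so it lowers the frequency without ruling the state out.

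Finally, the list was read from a PDF by a program. It reads as complete, but a lost line cannot be excluded.

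**Conclusion.** The point holds as a minor defect of the form as printed. Item IV lacks a level for giving way in daily activities that is less than frequent, and a subject in that state is mis-scored on a tested secondary endpoint.

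The combined size of the two possible errors, 10 points, follows from the printed boxes alone. The split into 5 and 5 rests on valuing the state at 10. The effect on an arm's mean change depends on how box choice varies between visits and on how many subjects are affected, which the documents do not give. The co-primary endpoints (WOMAC, VAS, MRI) are unaffected, and the study is described as proof of concept without a formal sample size calculation. The finding therefore warrants a check of the form and, if confirmed, a small correction. It does not call the trial's main conclusions into question.

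**What to change.** 1. Compare item IV in Appendix 5 and in the eCRF with the source version of the scale. If the level is present there and was lost only in the reading of the PDF, nothing further is needed.
2. If the level is absent from the form in use, insert the intermediate daily-activities level between the 15 and 5 boxes. Take its wording and value from the source: 10 points if the source confirms it. The maximum stays 100.
3. Use one form version per subject from baseline onward. A subject whose baseline was taken on the uncorrected form stays on that form, because switching would itself create artificial change.
4. For those subjects, report Lysholm with and without item IV, as a sensitivity analysis only. Dropping the item discards 25 of the 100 points, so it should not replace the planned analysis.

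The cost is one line on the form and one entry in the eCRF pick-list, plus a short sensitivity table if forms are already in use. Completed forms cannot be re-answered. Design, sample size and the rest of the analysis plan are unchanged.

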### V. PAIN:

- I have no pain in my knee. (25)
- I have intermittent or slight pain in my knee during vigorous activities. (20)
- I have marked pain in my knee during vigorous activities. (15)
- I have marked pain in my knee during or after walking more than 1 mile. (10)
- I have marked pain in my knee during or after walking less than 1 mile. (5)
- I constant pain in my knee. (0)

### VI. SWELLING:

- I have no swelling in my knee. (10)
- I have swelling in my knee only after vigorous activities. (6)
- I have swelling in my knee after ordinary activities. (2)
- I have swelling constantly in my knee. (0)

**VII. CLIMBING STAIRS:**

- I have no problems climbing stairs. (10)
- I have slight problems climbing stairs. (6)
- I can climb stairs only one at a time. (2)
- Climbing stairs is impossible for me. (0)

**VIII. SQUATTING:**

- I have no problems squatting. (5)
- I have slight problems squatting. (4)
- I cannot squat beyond a 90 degree bend in my knee. (2)
- Squatting is impossible because of my knee(s). (0)

Thank you very much for completing all the questions in this questionnaire.

---

**Score (by Study Coordinator):**

**TOTAL: \_\_\_\_\_ (Maximum: 100)**

Signature: \_\_\_\_\_ Date: \_\_\_\_\_

## Appendix 6. KOOS (Knee Injury & Osteoarthritis Outcome Score)

Site No: \_\_

Subject No: \_\_ \_\_

Subject Initials: \_\_ \_\_ \_\_

Visit (circle one): Baseline M1 M3 M6 M9 M12 ET ( / / ) Final FU ( / / )

### INSTRUCTIONS:

This survey asks for your view about your knee. This information will help us keep track of how you feel about your knee and how well you are able to perform your usual activities. Answer every question by ticking the appropriate box, only one box for each question. If you are unsure about how to answer a question, please give the best answer you can.

### SYMPTOMS

These questions should be answered thinking of your knee symptoms during the **last week**.

		0	1	2	3	4
S1	Do you have swelling in your knee?	 Never	 Rarely	 Sometimes	 Often	 Always
S2	Do you feel grinding, hear clicking or any other type of noise when your knee moves?	 Never	 Rarely	 Sometimes	 Often	 Always
S3	Does your knee catch or hang up when moving?	 Never	 Rarely	 Sometimes	 Often	 Always
S4	Can you straighten your knee fully?	 Never	 Rarely	 Sometimes	 Often	 Always
S5	Can you bend your knee fully?	 Never	 Rarely	 Sometimes	 Often	 Always

**Stiffness:** The following questions concern the amount of joint stiffness you have experienced during the **last week** in your knee. Stiffness is a sensation of restriction or slowness in the ease with which you move your knee joint.

		0	1	2	3	4
S6	How severe is your knee joint stiffness after first wakening in the morning?	 None	 Mild	 Moderate	 Severe	 Extreme
S7	How severe is your knee stiffness after sitting, lying or resting later in the day?	 None	 Mild	 Moderate	 Severe	 Extreme

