### 5) KOOS

① Change of KOOS from baseline at Month 6 (JointStem group vs. positive control group)  
; This secondary efficacy endpoint will be analyzed with an ANCOVA with factors of treatment and the baseline of KOOS as a covariate. Model-based LS Means of the differences between study and control groups, along with 95% CI and p-value will be provided.

② Change of KOOS from baseline at Months 6, 9 and 12 (JointStem group)

; Change of KOOS from baseline at Months 6, 9 and 12 will be analyzed using paired t-test. If change of KOOS from baseline at Months 6, 9 and 12 doesn't satisfy normal distribution, Wilcoxon signed rank test will be performed.

6) IKDC

- ① Change of IKDC from baseline at Month 6 (JointStem group vs. positive control group)  
; This secondary efficacy endpoint will be analyzed with an ANCOVA with factors of treatment and the baseline of IKDC as a covariate. Model-based LS Means of the differences between study and control groups, along with 95% CI and p-value will be provided.
- ② Change of IKDC from baseline at Months 6, 9 and 12 (JointStem group)  
; Change of IKDC from baseline at Months 6, 9 and 12 will be analyzed using paired t-test. If change of IKDC from baseline at Months 6, 9 and 12 doesn't satisfy normal distribution, Wilcoxon signed rank test will be performed.

7) RAND-36 Score

- ① Change of RAND-36 Score from baseline at Month 6 (JointStem group vs. positive control group)  
; This secondary efficacy endpoint will be analyzed with an ANCOVA with factors of treatment and the baseline of RAND-36 Score as a covariate. Model-based LS Means of the differences between study and control groups, along with 95% CI and p-value will be provided.
- ② Change of RAND-36 Score from baseline at Months 6, 9 and 12 (JointStem group)  
; Change of RAND-36 Score from baseline at Months 6, 9 and 12 will be analyzed using paired t-test. If change of RAND-36 Score from baseline at Months 6, 9 and 12 doesn't satisfy normal distribution, Wilcoxon signed rank test will be performed.

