### PAIN

		0	1	2	3	4
P1	How often do you experience knee pain?	 Never	 Monthly	 Weekly	 Daily	 Always

What amount of knee pain have you experienced the last week during the following activities?

		0	1	2	3	4
P2	Twisting/pivoting on your knee	 None	 Mild	 Moderate	 Severe	 Extreme
P3	Straightening knee fully	 None	 Mild	 Moderate	 Severe	 Extreme
P4	Bending knee fully	 None	 Mild	 Moderate	 Severe	 Extreme
P5	Walking on flat surface	 None	 Mild	 Moderate	 Severe	 Extreme
P6	Going up or down stairs	 None	 Mild	 Moderate	 Severe	 Extreme
P7	At night while in bed	 None	 Mild	 Moderate	 Severe	 Extreme
P8	Sitting or lying	 None	 Mild	 Moderate	 Severe	 Extreme
P9	Standing upright	 None	 Mild	 Moderate	 Severe	 Extreme

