### **Score (by Study Coordinator):**

KOOS Symptoms       $100 - (\text{Mean score of S1 to S7 } \underline{\hspace{2cm}} \times 25) = \underline{\hspace{2cm}}$

KOOS Pain       $100 - (\text{Mean score of P1 to P9 } \underline{\hspace{2cm}} \times 25) = \underline{\hspace{2cm}}$

KOOS ADL       $100 - (\text{Mean score of A1 to A17 } \underline{\hspace{2cm}} \times 25) = \underline{\hspace{2cm}}$

KOOS Sport/Rec       $100 - (\text{Mean score of SP1 to SP5 } \underline{\hspace{2cm}} \times 25) = \underline{\hspace{2cm}}$

KOOS QOL       $100 - (\text{Mean score of Q1 to Q4 } \underline{\hspace{2cm}} \times 25) = \underline{\hspace{2cm}}$

Signature: \_\_\_\_\_ Date: \_\_\_\_\_

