2. STATISTICAL METHODS

2.1 GENERAL CONSIDERATIONS

In general, continuous variables will be summarized by number of subjects, mean, SD, median, minimum, and maximum values. Categorical variables will be summarized by counts and percentage of subjects in each category. Source data for the summary tables and statistical analyses will be presented as subject data listings, which include data collected on the electronic case report forms (eCRFs) as well as any derived variables for all enrolled subjects.

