6.2.5 KOOS

KOOS (Symptoms, Pain, ADL, Sport/Rec, QOL) will be collected at Visits 3, 4, 5, 6, 7 and 8 (Baseline, M1, M3, M6, M9 and M12) or Early Termination (only if the subject is early terminated after Visit 3) or Final Follow-up Visit. Summary statistics of KOOS will be presented by visit and treatment group. The change from baseline will also be calculated and represented in summary table.

- ① Change of KOOS from baseline at Month 6 (JointStem group vs. positive control group)

This secondary efficacy endpoint will be analyzed with an ANCOVA with factors of

treatment and the baseline of KOOS as a covariate. Model-based LS Means of the differences between study and control groups, along with 95% CI and p-value will be provided.

② Change of KOOS from baseline at Months 6, 9 and 12 (JointStem group)

Change of KOOS from baseline at Months 6, 9 and 12 will be analyzed using paired t-test (two-sided test, $\alpha=0.05$) with the null hypothesis equal to zero. The number of patients, mean, standard deviation, minimum (min) and maximum (max) values for the baseline, months 6, months 9, months 12 and change from baseline will be calculated and reported in summary table. The p-value will also be provided. Shapiro-Wilks test will be used to test the normality of change of KOOS from baseline at Months 6, 9 and 12. If change of KOOS from baseline at Months 6, 9 and 12 doesn't satisfy normal distribution, Wilcoxon signed rank test will be performed.

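### The printed KOOS Symptoms rule counts full knee movement (items S4 and S5) as a symptom, so a perfect knee scores 71.4 and a symptom-free knee that never bends or straightens scores 100

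*Protocol*

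**What the plan says.** Protocol Appendix 6 prints the seven Symptoms items with codes 0 to 4. S1 to S5 share one set of responses, running from Never at 0 to Always at 4, and the labels are repeated on each row. S1 to S3 ask about swelling ("Do you have swelling in your knee"), noise and catching. S4 asks "Can you straighten your knee fully" and S5 asks "Can you bend your knee fully". S6 and S7 rate stiffness from None at 0 to Extreme at 4.

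The scoring block at the end of Appendix 6, which the study coordinator completes, defines the subscale as 100 minus 25 times the "Mean score of S1 to S7". All seven items enter the mean in the same way.

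Protocol 6.1.5 makes "Change of KOOS from baseline at Month 6 (JointStem group vs. positive control group" a secondary comparison by ANCOVA with baseline KOOS as covariate, and adds within-group tests in the JointStem arm at Months 6, 9 and 12. SAP 6.2.5 repeats these analyses and names the subscales: "KOOS (Symptoms, Pain, ADL, Sport/Rec, QOL) will be collected". Neither section mentions reversing any item. SAP 2.1 says that listings will hold eCRF data "as well as any derived variables for all enrolled subjects", but does not show how the KOOS variables are derived.

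**The concern.** Because the formula subtracts the mean, a higher code always lowers the score. That suits S1 to S3, S6 and S7, where 4 is the worst state. It does not suit S4 and S5, where 4 means that the knee always straightens or bends fully. Every other KOOS item on the form, in all five subscales, runs from good at 0 to bad at 4. S4 and S5 are the only two that run against the formula.

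The attainable range is still 0 to 100, so implausible totals would not reveal the error. What goes wrong is the ordering: stiffer knees can score better than freely moving ones.

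At stake are the KOOS Symptoms results: the between-arm ANCOVA at Month 6, where both the outcome and the baseline covariate would be mis-scored, and the JointStem tests at Months 6, 9 and 12. Secondary tests are each done at the 5% level (Protocol 6.1.3, SAP 6), with 20 and 10 subjects planned per arm.

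**Working it through.** The plan gives no worked KOOS score, so there is no stated figure to reproduce. The inputs are the item codes and the scoring line in Appendix 6.

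**Two versions of the score**

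- As printed: 100 − 25 × (S1 + S2 + S3 + S4 + S5 + S6 + S7) / 7
- Aligned: the same, with S4 and S5 replaced by 4 − S4 and 4 − S5

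**Four limiting knees** (codes in order S1 to S7)

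| Knee | Codes | As printed | Aligned |
|---|---|---|---|
| Perfect | 0,0,0,4,4,0,0 | 100 − 25×8/7 = 71.4 | 100 |
| No symptoms, never straightens or bends | 0,0,0,0,0,0,0 | 100 | 100 − 25×8/7 = 71.4 |
| Worst on every item | 4,4,4,0,0,4,4 | 100 − 25×20/7 = 28.6 | 0 |
| All symptoms at worst, always straightens and bends | 4,4,4,4,4,4,4 | 0 | 100 − 25×20/7 = 28.6 |

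From the worst knee to the perfect knee the printed score spans 71.43 − 28.57 = 42.86 points instead of 100.

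**Error in level.** Printed minus aligned = −(25/7) × (2(S4 + S5) − 8) = 7.14 × (4 − (S4 + S5)). This runs from +28.6 when both codes are 0 to −28.6 when both are 4. It is zero only when the two codes sum to 4.

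**Error in change.** Differencing two visits leaves −(50/7) = −7.14 points per category gained on S4 or S5.

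| Change between visits | As printed | Aligned |
|---|---|---|
| All seven items improve one category | 25×(5−2)/7 = +10.7 | 25×7/7 = +25 |
| Only S4 and S5 improve one category | −25×2/7 = −7.1 | +7.1 |
| Other five improve one, S4 and S5 worsen one | 25×(5+2)/7 = +25 | 25×(5−2)/7 = +10.7 |
| One other item improves one, S4 and S5 worsen one | 25×(1+2)/7 = +10.7 | 25×(1−2)/7 = −3.6 |

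So if S4 and S5 improve along with the other items, improvement is understated and can change sign. If they worsen while the others improve, improvement is overstated, and a true decline can appear as a gain. If their sum does not change, the change score is right, although the level is wrong unless that sum is 4.

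**Between arms.** For the unadjusted difference in mean change, the error is −7.14 times the between-arm difference in mean change of S4 + S5. The ANCOVA estimate also depends on the mis-scored baseline, so it is not a simple multiple of that quantity.

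**Comparison within the protocol.** Pain items P3, "Straightening knee fully", and P4, its bending counterpart, run from None at 0 to Extreme at 4, in line with the formula. A one-category gain on both raises KOOS Pain by 25×2/9 = 5.6 points, whereas a one-category gain on S4 and S5 lowers Symptoms by 7.1. The RAND-36 form in Appendix 8 also mixes item directions, and its scoring table gives the recoding item by item. Appendix 6 has no such table.

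**The case against.** The strongest reply is that the reversal may exist where we cannot see it. SAP section 1 says the plan was developed from the protocol and the eCRFs, and the SAP gives no scoring rule for WOMAC, Lysholm, IKDC or RAND-36 either. Its silence on S4 and S5 therefore does not show that the programs omit a reversal. This stands, and it confines the finding to the written rule. It does not remove the finding: that rule is the only one in the documents, and the site coordinator is asked to apply it by hand.

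Further points:

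- **Extreme cases.** The limiting knees are unlike the enrolled population, which has Kellgren-Lawrence grade 3 to 4 disease and pain of at least 40 mm. That is fair. The ±28.6 range is a bound, not an estimate, and the documents give no expected distribution of S4 and S5.
- **Subscale testing.** The plan specifies tests of KOOS, not explicitly of each subscale. Testing Symptoms separately is an inference, but no KOOS total is defined and Appendix 6 ends in five subscale scores, so no other reading is workable.
- **Pain items.** P3 and P4 rate pain during movement, not how often full movement is possible. They are a different construct and serve only as an illustration; the case does not depend on them.
- **Weight.** One subscale of one of six between-arm secondary measures is affected, in a study with no formal sample size calculation. That limits the severity, not the correctness.

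A PDF-reading fault is an unlikely explanation, because the response labels are printed separately on the S4 and S5 rows.

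**Conclusion.** The concern holds. This is an error in the written scoring rule, not merely a missing detail: applied literally, Appendix 6 ranks knees in the wrong order on the two movement items. It follows from the printed codes and formula alone and needs no outside scoring manual.

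Confidence is high for the rule as written. Nothing can be said about the trial's data, because that depends on the eCRF, the programs and how S4 and S5 moved. Pain, ADL, Sport/Rec and QOL are scored consistently, and the WOMAC, VAS, MRI and safety analyses are untouched. It should be fixed before KOOS is analysed, but it does not bear on the primary conclusions.

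**What to change.** 1. Check first whether the eCRF or the analysis program already reverses S4 and S5, so that they are not reversed twice.
2. Add one sentence to Appendix 6 and to SAP 6.2.5: S4 and S5 are scored as 4 minus the printed code before the mean of S1 to S7 is taken.
3. Derive the subscale at every visit from item responses rather than from the coordinator's hand total, and re-score forms already totalled.
4. Preferably keep the printed response layout. Reprinting the boxes in reverse order would also work, but risks two coding conventions in one dataset.

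The cost is two sentences, one check and the re-derivation of one subscale, with no new assessments of subjects. The documents do not say whether item responses or only totals are entered. If only totals are held, the Symptoms items would have to be entered from the retained source forms.
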